### 4.2 Study design

#### 4.2.a. Narrative study description (of the protocol)

We propose an 8 week, 3-arm randomized clinical trial to pilot test two interventions, Smoke Sense and Smoke Sense Plus, in comparison to a control group among young adults with asthma. This research design enables an examination of feasibility and acceptability of processes that are key to the success of a future trial. The design also enables us to estimate the effect size of the Smoke Sense interventions on primary (lung function, asthma control, asthma quality of life) and secondary outcomes of interest (anxiety, exposure reduction behaviors, and symptom mitigating behaviors), as compared to a control group, among young adults with asthma. Measures will be assessed at baseline, 4 and 8 weeks. The intervention period is 8 weeks. The sample will consist of 60 young adults, 18-26, with diagnosed asthma (of any type). Study activities will take place during wildfire season, July-October. To be included in the study, participants will need to have been diagnosed by a health care provider as having asthma, own a smart phone (Android or iOS platforms), speak and read English, and reside in Spokane County, WA. People can not be in the study if they are a Smoke Sense app user, have had surgery within 3 weeks of enrollment, or a cardio-vascular condition, both of which are contraindications for spirometry.

The choice of sample size (n=60 participants) was based on achieving Aim 1, focusing on assessment of the feasibility and acceptability of the Smoke Sense interventions. *Feasibility.* We expect that the true consent rate of eligible young adults is 75%. To test this, we will recruit up to 86 eligible individuals. There is an 89% probability that 60 or more of these individuals will consent to participate if the true consent rate is 75% (based on the cumulative binomial probability). We expect that the true rate of completion of the week-8 assessment is 80%. If this is correct, there is an 87% probability that we will observe at least 45 out of 60 participants completing the week-8 assessment. Similarly, we expect that the true rate of completion of the week-8 assessment is 75%. If this is correct, there is an 85% probability that we will observe at least 42 out of 60 participants completing the week-8 assessment.

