**Acceptability.** We hypothesize that the true intervention adherence (adoption) rate for the two intervention groups is 70% and 85%, Smoke Sense and Smoke Sense Plus, respectively. If this is correct, there is an 87% probability that we will observe that at least 12 out of 20 participants will adhere to Smoke Sense. There is a 93% probability that we will observe at least 15 out of 20 participants will adhere to or Smoke Sense Plus.

Young adults will be recruited from Washington State University-Spokane, and the Community Colleges of Spokane. (See LOS). Recruitment messages will be posted to social media sites and sent via the respective student affairs offices and health clinics to student list servs. A phone screening will determine study eligibility. If eligible, we will invite participants to the clinical laboratory at WSU Spokane for study visit 1 (Timepoint 1). Research personnel will consent the participant.

Eligible young adults will be randomized with equal probability to 1 of 3 study groups in blocks of 2, 4 and 5. Random assignment of the 60 participants will be determined by [name] using a randomization software. Random group assignment and a corresponding unique study identification (ID) number will be placed in sealed envelopes that are numbered sequentially from 1-60. After the consent is signed, research personnel will open the envelope to reveal the participant's group assignment. Research personnel will record the participant's name, study ID and group assignment in a password protected spreadsheet stored on a secure server at WSU. As part of the training, participants will download the appropriate app to their mobile phones. A set-up macro will ask the participant to enter their study ID which can be associated with all study data captured by the app.

A phone screening will determine study eligibility. If eligible, we will invite participants to the clinical laboratory at WSU Spokane for visit 1 (T1). A research assistant (RA) will consent and randomize the participant but the investigative team will be blinded to group assignment.

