restrictions in range and achievement of MID for each outcome. Generalized linear mixed models (GLMMs) will be fit that include main effects for study group and time point (1=baseline, 2=4 weeks, T3=8 weeks) and the interaction. An identity (continuous outcome) or logit (binary outcome) link function will be specified using SAS 9.4 PROC GLMMIX. Correlations within-participant over repeated measures of time will be controlled for using a random intercept model and a variance component covariate structure. The interaction terms and the slope coefficients for the 3 study groups will be of central interest to characterize changes in each of the outcomes across time. The same analytic approaches will be applied to the secondary (self-report) outcomes including anxiety, exposure reduction behaviors, and mitigating behaviors. Objective measures of exposure reduction behaviors will be estimated using GPS data. To examine the association between each of the GPS-based behaviors and study group during periods of poor AQ, full factorial GLMMs will be fit that include group, day, AQ (1=poor or worse, 0=normal) and specify a random intercept model with an autoregressive covariance structure.

Analyses will examine if the efficacy of the Smoke Sense interventions on outcomes is mediated (adherence to medication therapy, level of self-management skills, and psychological stress) or moderated (asthma severity/control) (Aim 3). For the mediation analyses, PROC CAUSALMED will be used for bootstrapping the CIs of the indirect effects or p-values for the corresponding tests. For moderation by asthma severity/control, we will run the same set of analyses proposed for Aim 2, now including an additional main effect of asthma severity/control and an interaction term of asthma severity/control by study group. We will graph the means of each outcome across subgroups to better understand what, if any, interaction is present. For Aims 2 and 3, two-sided statistical tests will be performed (alpha=0.05). The results from all of the statistical tests performed in Aims 2 and 3 will be interpreted as hypothesis-generating for a future R01 grant submission.

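### The GPS model lets participants differ in average behavior but not in their response to poor air quality, so its group-by-AQ intervals are too narrow if responses vary

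*Combined protocol and SAP*

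**What the plan says.** In the combined protocol and SAP, section 4.4 (Analytic plan), the GPS analysis is introduced with this purpose: "To examine the association between each of the GPS-based behaviors and study group during periods of poor AQ". The fixed effects are group, day and a binary AQ indicator, fully crossed, so the model contains a group-by-AQ term. For the covariance, the plan will "specify a random intercept model with an autoregressive covariance structure". It mentions no random AQ slope, robust standard error or degrees-of-freedom method for this model, and it does not say which contrast answers the question.

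Aim 2 and 3 tests are two-sided at 0.05 and "will be interpreted as hypothesis-generating for a future R01 grant submission". Section 4.1 lists exposure reduction behaviors as secondary outcomes, and section 4.4 makes GPS the source of their objective measures.

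**The concern.** Group varies between people; AQ varies from day to day within a person. Group-by-AQ is therefore a cross-level interaction: it compares arms on how much their members change when the air is poor. Its error term has to include the spread of that change between people, on about 60 - 3 = 57 degrees of freedom.

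The planned structure omits that spread. The random intercept covers differences in average behavior, and the autoregressive term covers carry-over from one day to the next. The interaction is then judged against daily noise from up to 60 x 56 = 3,360 records, as if everyone reacted alike.

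The plan itself gives reason to expect unequal reactions. It proposes moderation by asthma severity or control, and it expects adherence of 70% and 85% in the two intervention arms. Section 4.1 also says that the treatment effect and its variance will be examined for a future trial, and an omitted variance component distorts that product directly.

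**Working it through.** **Figures in the plan.** The documents give no standard error, power or error rate for the GPS model beyond the nominal alpha of 0.05. The only reproducible figures are the Aim 1 binomial probabilities (stated 89, 87, 85, 87 and 93%; exact 89.2, 86.9, 85.1, 88.7 and 93.3%). They do not bear on this model.

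**Inputs from the documents**
- 60 participants; "Eligible young adults will be randomized with equal probability to 1 of 3 study groups", so about 20 per arm (section 4.2.a).
- "The intervention period is 8 weeks" (section 4.2.a), taken as T = 56 days. Section 4.1 speaks of a 3-month study period.
- All participants live in one county, so poor-AQ days are taken as common to everyone.

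**Assumed inputs (not in the documents)**
- Continuous outcome with daily SD 1, complete GPS data, intercept SD 0.7 and lag-1 correlation 0.3.
- m = 14 poor-AQ days.
- Between-person SD of the AQ response, s = 0, 0.2, 0.3 or 0.5.

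**Step 1: hand calculation without carry-over.** Let D be a participant's mean on poor-AQ days minus the mean on normal days.
- Variance the planned model recognizes: 1/m + 1/(T - m) = 1/14 + 1/42 = 0.0952.
- Actual variance: 0.0952 + s².
- Ratio: k = 1 + s²/0.0952. The number per arm cancels.
- Pairwise error: 2[1 - Φ(1.96/√k)].
- 2-df error: exp(-5.991/(2k)).

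This ignores the small part of s² that the fitted residual variance absorbs.

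| s | k | √k | Pairwise | 2-df |
|---|---|---|---|---|
| 0 | 1 | 1 | 5% | 5% |
| 0.2 | 1.42 | 1.19 | 10% | 12% |
| 0.3 | 1.945 | 1.39 | 16% | 21% |
| 0.5 | 3.625 | 1.90 | 30% | 44% |

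**Step 2: with carry-over.** A large-sample calculation with the planned random intercept plus autoregressive covariance gives:

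| s | Two 7-day episodes: pairwise / 2-df | Scattered days: pairwise / 2-df |
|---|---|---|
| 0 | 5% / 5% | 5% / 5% |
| 0.2 | 8% / 9% | 12% / 15% |
| 0.3 | 12% / 15% | 19% / 26% |
| 0.5 | 22% / 31% | 34% / 50% |

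The hand figures lie between the two patterns, as they should. Carry-over makes a block mean noisier, so s² matters relatively less. It makes scattered-day comparisons more precise, so s² matters more.

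**Step 3: few poor-AQ days.** For one 4-day episode, 1/4 + 1/52 = 0.269, so at s = 0.5 k = 1 + 0.25/0.269 = 1.93 and the pairwise error is about 16% without carry-over. With carry-over the pairwise figure is about 6-13% over s = 0.2 to 0.5.

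**Step 4: group contrast at AQ = 1.** The planned model already counts the intercept variance here. Without carry-over, a participant's poor-day mean has recognized variance 0.7² + 1/14 = 0.561 and actual variance 0.561 + s².
- s = 0.2: ratio 1.07, error 6%.
- s = 0.3: ratio 1.16, error 7%.
- s = 0.5: ratio 1.45, error 10%.

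**Step 5: simulation.** These runs used 400 null trials per cell, REML, intercept SD 1, correlation 0.2 to 0.6, and 8 to 16 poor-AQ days in two blocks. Monte Carlo error is about 1 point near 5%.
- Pairwise group-by-AQ error: 4-6% at s = 0, 8-14% at s = 0.25 and 20-27% at s = 0.5.
- 2-df test at the same values: 4-6%, 10-16% and 25-35%.
- Group contrast at AQ = 1: about 5-6% up to s = 0.25 and 7-8% at s = 0.5.
- Adding day terms and their interactions did not cure the problem: 22% pairwise at s = 0.5.

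**Step 6: remedy.** With a random AQ slope and 57 degrees of freedom, pairwise error at s = 0, 0.5 and 1.0 was 4.2%, 5.0% and 3.8%; the 2-df test gave 3.2%, 4.8% and 4.0%. Comparing arms on one difference per person gave 3-7% in every setting tried.

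**The case against.** The strongest reply is that the plan asks how behavior relates to group during poor AQ, which reads naturally as the arm difference on poor-AQ days. For that contrast the random intercept already supplies person-level error, and the inflation is mild. This stands as one reading. It does not settle the matter, because a full factorial model also contains group-by-AQ, the term that separates a response to smoke from a general difference in mobility. The plan does not say which is meant.

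The size also rests on assumptions. The documents give no response spread, autocorrelation, number of poor-AQ days or scale for the GPS behaviors. Wildfire smoke more plausibly comes in episodes than on scattered days, and the plan itself allows for an unusually clean season. Section 4.4 expects 80% and 75% completion at T3 and T4, so GPS records will be incomplete; fewer days per person would reduce the inflation. The rates may not carry over to binary or count measures. All of this stands and limits the size, not the mechanism.

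A reader might infer that the standard error is certainly too small, or that the trial faces an error rate near 50%. Neither follows: with equal responses the model holds 5%, and the top figure needs the largest assumed spread, scattered days and the joint test. Nor do the documents support reading this as a threat of a false efficacy claim. The outcome is secondary, the tests are declared hypothesis-generating, and the sample size rests on Aim 1 feasibility.

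**Conclusion.** The point holds conditionally. The planned GPS model has no participant-level variation in the response to poor AQ, and nothing else in the documents guards against it. If responses vary, group-by-AQ intervals are too narrow. For a response SD of 0.2 to 0.5 daily SDs under the assumptions above, pairwise error is roughly 8-22% with episodic smoke, 12-34% with scattered days and 6-13% with one short episode. For the group contrast at AQ = 1 it is about 6-10%. A larger spread would give more; none gives 5%.

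The consequence is overconfident intervals and an incomplete variance estimate for an exploratory secondary outcome, passed on to the design of the next trial. That merits correction before analysis but does not undermine the pilot's feasibility aim.

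**What to change.** In section 4.4:
1. Name the GPS contrast of interest: group-by-AQ, or group at AQ = 1.
2. Add a participant-level random slope for AQ, with an unstructured 2x2 covariance with the intercept, and test the contrast on person-level degrees of freedom.
3. State a fallback if the slope cannot be estimated. For group-by-AQ, compare arms on each participant's mean on poor-AQ days minus the mean on normal days. Alternatively, use participant-clustered robust standard errors with a small-sample correction.

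The cost is one extra random term and two or three sentences, with no new data or procedures. Intervals will be somewhat wider if responses vary, and the model may fail to converge when poor-AQ days are few, which the fallback covers. If responses do not vary, little is lost: pairwise error with the slope included was 4.2%.

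### The Aim 3 severity-by-group term averages in the pre-intervention visit, so with complete visits it estimates two thirds of the average post-baseline moderation effect

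*Combined protocol and SAP*

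**What the plan says.** Everything is in section 4.4, Analytic plan, unless noted.

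- The Aim 2 model contains "main effects for study group and time point (1=baseline, 2=4 weeks, T3=8 weeks) and the interaction", with a random intercept. Baseline is therefore a row of the response, not a covariate. Section 4.2.a agrees on the schedule: "Measures will be assessed at baseline, 4 and 8 weeks".
- For Aim 2, "The interaction terms and the slope coefficients for the 3 study groups will be of central interest", so the effect of interest is change over time by group.
- For moderation, the Aim 2 model is carried over: "we will run the same set of analyses proposed for Aim 2". Only two terms are then listed as additions to it, in these words: "including an additional main effect of asthma severity/control and an interaction term of asthma severity/control by study group". No severity-by-time term, no severity-by-group-by-time term and no baseline adjustment is named. The full factorial specification is given only for the GPS models.
- Aim 3 asks whether the efficacy of the interventions is moderated. Its results are to be "interpreted as hypothesis-generating for a future R01 grant submission".
- The plan does not say when severity/control is measured for use as a moderator.

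**The concern.** A severity-by-group term with no time component is constant over visits. The group-by-time effect, which carries the intervention effect, is then forced to be the same at every level of severity. Moderation can enter only as a difference in level shared by all three visits, one of which precedes the intervention. At that visit the differential effect is zero apart from chance imbalance, so the coefficient is pulled toward zero.

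At stake is the size of the moderation signal taken forward to a future trial. A differential as large as the 3-point minimally important difference given for the Asthma Control Test (ACT) in section 4.3 would be expected to appear as about 2 points.

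The point covers continuous outcomes measured at baseline, week 4 and week 8, with a moderator fixed at baseline. It does not cover the GPS models, the binary (logit) outcomes or a time-varying moderator.

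**Working it through.** The plan gives no effect size, SD, correlation or power for moderation, so there is no figure of its own to reproduce.

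**Inputs from the plan.** Three visits, one of them pre-intervention; random intercept and identity link; 60 participants in three equal groups; ACT minimally important difference 3 points. Section 4.2.a gives completion rates of 80% and 75%, both for week 8; the Sample Size Justification in section 4.4 gives the same rates for T3 and T4. No week-4 rate is stated.

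**Assumptions.** Moderator fixed at baseline. For the precision figures, binary severity split evenly (10 per severity-by-group cell) and total SD 1. Equal within-person correlation rho of 0.1–0.7. Dropout monotone and unrelated to arm or severity. Week-8 completion 75–80%, and week-4 completion between that rate and 100%.

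**1. Complete visits.** Let the differential effect be (0, d4, d8). A time-constant term in a random-intercept model is estimated from each participant's three-visit mean, so its expectation is

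(0 + d4 + d8)/3 = (2/3) × (d4 + d8)/2.

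- (0, 3, 3) gives 2.0 against a post-baseline average of 3.
- (0, 2, 4) gives 2.0 against 3.
- (0, 0, 3) gives 1.0 against 1.5.

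Exact generalized least squares on the full three-arm model gave 0.667 each time, whatever the correlation, whether time was categorical or linear, and whether the moderator was binary or continuous. If a T4 visit were also modelled, the share would be 3/4.

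**2. Dropout.** With p_k the proportion having k visits observed, w_k = 1/(1 + (k−1)rho), and the sum of d taken over the observed visits, the expectation is

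Σ p_k w_k (sum of d) / Σ p_k w_k k.

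Example: 75% complete all visits, 25% have baseline only, rho = 0.1. Then w_3 = 1/1.2 = 0.833, and the share for an equal effect is (0.75 × 0.833 × 2)/(0.75 × 0.833 × 3 + 0.25) = 1.25/2.125 = 0.588.

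Shares for an effect equal at both follow-ups:

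| Week-4, week-8 completion | rho 0.1 | 0.25 | 0.5 | 0.7 |
|---|---|---|---|---|
| 75%, 75% | 0.588 | 0.571 | 0.545 | 0.526 |
| 100%, 75% | 0.634 | 0.632 | 0.629 | 0.627 |
| 80%, 80% | 0.606 | 0.593 | 0.571 | 0.556 |
| 100%, 80% | 0.641 | 0.639 | 0.636 | 0.635 |

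A 3-point differential would thus be estimated as 3 × 0.526 = 1.6 to 3 × 0.641 = 1.9. Dropout does not always lower the share: for an effect at week 4 only, with full week-4 attendance, it is 0.72–0.75.

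**3. Precision, complete visits.** Three forms are compared: the planned term; a preferred form (weeks 4 and 8 as response, baseline outcome as covariate); and an alternative (baseline kept in the response, averaged post-baseline three-way contrast). Per-participant variances are

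- planned: rho + (1 − rho)/3
- preferred: (1 − rho)(1 + 2rho)/2
- alternative: 1.5(1 − rho)

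The contrast involves four cells of 10, so SE = √(4 × variance/10). For example, at rho 0.1 the SEs are √(0.4 × 0.40) = 0.400 (planned) and √(0.4 × 0.54) = 0.465 (preferred). For a true differential of 1 SD at both follow-ups, using the noncentral t with 54, 53 and 54 df:

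| rho | Power: planned / preferred / alternative | Planned 95% interval covers 1 SD |
|---|---|---|
| 0.1 | 37 / 56 / 27% | 87% |
| 0.25 | 31 / 54 / 31% | 89% |
| 0.5 | 25 / 59 / 43% | 90% |
| 0.7 | 21 / 73 / 64% | 91% |

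Simulation (10,000 runs per row) gave a mean of 0.66–0.67 for the planned term and 0.99–1.00 for the preferred form. Coverage of the true effect by the preferred form was 94.5–95.3%. The planned term rejected a true null 4.5–5.3% of the time.

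**The case against.** The strongest case against has four parts.

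- **The premise is partly assumed.** The timing of the moderator is not stated, ACT control is measured repeatedly, and the list of added terms might not be meant as complete. The first two are true, which is why the result is conditional and why the fix starts by defining the moderator. On the third, the plan names the added terms and none involves time; following the text produces the averaged term.
- **The visit structure is unsettled.** Other sections use T1–T4, and spirometry in Smoke Sense Plus is described as daily in section 4.2.a and weekly in section 4.2.c. The stated model nevertheless has three time points. A fourth changes 2/3 to 3/4; spirometry analysed at more occasions would give another share.
- **The preferred repair also has a time-constant term.** This is correct. With full week-4 attendance and 75–80% at week 8, it gives 0.81–0.88 of the average effect if the effect is at week 8 only, and 1.12–1.19 if at week 4 only. The planned term gives 0.51–0.56 and 0.72–0.75 in the same cases, so the repair is closer in both. The three-way model fits better with the plan's emphasis on change over time, but is less precise at low correlation.
- **The stakes are low.** Aim 3 is hypothesis-generating, n=60 was chosen for Aim 1, and subgroup means will be graphed. For a small differential of 0.3 SD, the planned term has lower root mean squared error than the preferred form at rho 0.1 (0.41 against 0.47) and 0.25 (0.46 against 0.47), though not at 0.5 or 0.7. This limits the consequence. It does not change what the coefficient estimates, and the graphs do not correct the coefficient, its interval or its test.

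**Conclusion.** The concern holds. For continuous three-visit outcomes and a baseline moderator, the planned term estimates 2/3 of the average post-baseline differential when visits are complete, whatever the split between weeks 4 and 8. It estimates 0.53–0.64 of it under the dropout range above when the effect is equal at both follow-ups.

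Against the week-8 effect alone, which the plan does not name as its moderation target, the complete-visit share is 2/3, 1/2, 1/3 or 1.0 when the week-4 effect is respectively equal to, half of, zero, or twice the week-8 effect.

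The complete-visit share needs no assumption about the correlation. The dropout and precision figures rest on the assumed correlations, week-4 attendance and, for precision, the even severity split. The error is attenuation and lost power, not false positives. It should be corrected, but it does not threaten the trial's main purpose.

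**What to change.** State that the moderator is the severity/control value at baseline. Then choose one of two forms for continuous outcomes.

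**Preferred.** Model the week-4 and week-8 outcomes with group, time, group-by-time, severity, severity-by-group and the baseline outcome as covariate. When ACT is the outcome, use baseline ACT as covariate or moderator only in this form, where baseline is not part of the response.

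**Alternative.** Keep baseline in the response, add severity-by-time and severity-by-group-by-time, and read moderation from the three-way contrast averaged over weeks 4 and 8.

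**Cost.** One or two SAP sentences; no new data or visits. With binary severity the fixed parameters number 12 as planned, 10 preferred and 18 alternative.

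- *Preferred, complete visits:* the interval is 16% and 6% wider than the planned term's at rho 0.1 and 0.25, and 13% and 33% narrower at 0.5 and 0.7.
- *Preferred, with the dropout range above:* 18–24% and 8–15% wider, then 4–11% and 24–31% narrower. For an effect equal at both follow-ups its signal-to-noise exceeds the planned term's throughout (planned/preferred 0.40–0.76). Participants with no follow-up visit contribute nothing.
- *Alternative, complete visits:* 84%, 50% and 6% wider at rho 0.1, 0.25 and 0.5, and 25% narrower at 0.7. Its signal-to-noise is lower than the planned term's below rho 0.25 with complete visits, and at rho 0.1 with dropout.

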Participants will fill out a series of questionnaires via a link sent to their phone. The RA will weigh and measure the participant. The RA will train the participant on the use of a portable digital spirometer with a mouthpiece that connects to the participant's smartphone. The participant will download spirometry software onto their phone and enter their age, sex, height and weight. Participants will be asked to practice exhaling into the mouthpiece. This air turns a motor while the device registers the speed, adapts it and transfers the measurement to the participants' smartphone application. When a participant initiates exhalation, a chronometer changes from red to green after 6 seconds of exhalation. Users can visualize their exhalation curve via the color change and see if they have made an error. The device will select the best result out of 3 attempts. Participants will be asked to return-demonstrate the process until they have definitive results. No calibration is required. Participants will also receive a GPS device and will be instructed on its continuous use during waking hours. Participants will be told that they will be sent an email with a link to a suite of Qualtrics' surveys, which they will be asked to complete via their phone at T2, T3 and T4. Participants in both intervention groups will be instructed on how to download and use the Smoke Sense app. Participants will be asked to return to the clinical lab so research personnel can download their GPS data at T2, T3 and T4. At T4 they will return their spirometer and GPS unit, and complete the System Usability Scale and the Research Attitudes Questionnaire. They can earn \$150, in \$50 increments, per visit, T2-T4.

This study proposes 2 intervention groups: Smoke Sense and Smoke Sense Plus. Smoke Sense Plus offers potentially value-added preventive activities to Smoke Sense. We hypothesize that with these additional activities, users will take actions to reduce their exposure before experiencing symptoms and reduce the severity of outcomes.

Upon downloading, the Smoke Sense mobile app prompts users to set up a Profile, which includes a zip code, demographic information (sex, age, race, education level), baseline health information (pre-existing conditions, physical activity level, time spent outdoors), and beliefs about smoke and air pollution (e.g. Does smoke impact health?). In the Symptoms & Smoke

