Observations tab, participants report their weekly observations of smoke, health symptoms, and exposure reduction behaviors. Four symptom categories are reported, eyes and ears, respiratory, cardiovascular, and/or other, as well as the severity of adverse health effects (i.e. symptom duration, whether medication was used, and whether an unplanned trip to a health care provider occurred). In the Fire & Smoke Near Me tab, participants can look at current AQ data measured at monitoring sites and future forecasts. The AQ 101 module leads to trivia games which test knowledge of AQ facts and provides correct answers. Badges are awarded for accomplishments to promote desired behaviors: completing a user profile, launching the app weekly to check local AQ, reporting smoke and symptom observations, expanding AQ knowledge with AQ lessons, and exploring the map. Finally, participants can engage with other users by viewing cumulative statistics of symptoms and smoke observations.

Participants randomized to Smoke Sense Plus will be asked to engage in the Smoke Sense app, as well as additional, evidence-based activities, including: 1) Receive weekly, push notifications that remind them to, for example, review their asthma action plan, take their daily controller medication, refill any expired medications, and identify places to go with filtered indoor air (e.g. library), 2) Monitor lung function daily using a portable spirometer, and 3) Subscribe to a social network to share spirometry data, and exposure reduction strategies. Both interventions will be delivered via participants' smart phones.

The control group will receive incentives for study participation but will not be introduced to the Smoke Sense app.

4.2.b Purpose: PREVENTION

4.2.c Intervention Type: behavioral

IVN Name: Smoke Sense

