**Potential problems and alternative strategies.** Age could be broadened if recruitment is a challenge. If AQ is uncharacteristically healthy during the study period, we will use WSU-

Extension to recruit in areas with poor AQ. Data collection may influence behavior change. To examine this, we will assess matched outcomes among national Smoke Sense users and our control group. While not feasible in this study, we will include a future attention control group. Use of spirometry may decrease the magnitude of the interventions' effect. However, the benefits of measuring lung function objectively outweigh the potential decrease in effect sizes.

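### The planned check for measurement reactivity compares app users with a no-app control arm, so it mixes the data-collection effect with the app effect and cannot by itself show reactivity

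*Combined protocol and SAP*

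**What the plan says.** The paragraph on potential problems and alternative strategies in section 4.4 names the risk: "Data collection may influence behavior change". The next sentence gives the check: "To examine this, we will assess matched outcomes among national Smoke Sense users and our control group". It then defers the design solution: "While not feasible in this study, we will include a future attention control group".

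Section 4.2.a fixes what each group receives.

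- **Control arm, app:** none. "The control group will receive incentives for study participation but will not be introduced to the Smoke Sense app". Existing users are also barred at entry: "People can not be in the study if they are a Smoke Sense app user".
- **Trial participants, data collection:** described for participants generally, without restriction by arm. "Participants will also receive a GPS device and will be instructed on its continuous use during waking hours". On spirometry, "The RA will train the participant on the use of a portable digital spirometer with a mouthpiece". Phone questionnaires and repeat laboratory visits are described in the same way.
- **App users:** in one tab of the app, "participants report their weekly observations of smoke, health symptoms, and exposure reduction behaviors". No trial data collection is described for national users.

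The documents give no matching variables, outcome list, model or rule of interpretation for this check.

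**The concern.** The question is whether being measured changes what participants do. To answer it, two groups should differ in trial data collection and be alike in app exposure. The two groups named differ in both, in opposite directions: one has the app without the trial's measurements, the other has the measurements without the app.

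This is the only reactivity check planned for this study, since an attention control is said not to be feasible here. The same paragraph concedes that spirometry may shrink the interventions' effects, so reactivity bears on how the pilot's effect estimates are read. As written, the plan promises an answer that the comparison cannot give.

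**Working it through.** The plan states no figure for this check, so there is none to reproduce. The test is whether the planned contrast identifies the quantity of interest.

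**Notation.** R is the effect of trial data collection, A the effect of the app, and S the difference between trial participants and national users that remains after matching. Effects are taken as additive (an assumption).

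**Step 1. What each group carries (section 4.2.a).**

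| Group | App | Trial data collection | Expected outcome, relative to an unmeasured national non-user |
|---|---|---|---|
| National app users | yes | none described | A |
| Control arm | no | yes | R + S |
| Trial Smoke Sense arm | yes | yes | A + R + S |

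**Step 2. Contrasts.**

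- Planned: control arm minus national users = (R + S) - A = R - A + S.
- Like for like: trial Smoke Sense arm minus national users = (A + R + S) - A = R + S.

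The planned contrast is one equation in R and A even when S = 0, so R is not identified. Matching can reduce S. It cannot remove A, because app exposure differs between these two groups by design.

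**Step 3. Illustration.** The documents give no values for A, R or S. The values below are assumed, in SD units, with A and R at 0 or 0.3.

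| A | R | S | Planned, R - A + S | Like for like, R + S |
|---|---|---|---|---|
| 0 | 0 | 0 | 0 | 0 |
| 0.3 | 0.3 | 0 | 0 | 0.3 |
| 0.3 | 0 | 0 | -0.3 | 0 |
| 0 | 0.3 | 0 | 0.3 | 0.3 |
| 0 | 0 | 0.3 | 0.3 | 0.3 |

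Rows 1 and 2 give the same planned result with and without reactivity. Row 3 gives a difference with no reactivity. Row 5 shows the limit of the alternative: residual selection looks the same as reactivity in either contrast.

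**Step 4. Precision.** Sixty participants in three equal arms give 60/3 = 20 per arm. Take a continuous outcome with SD 1, one time point, full follow-up and so many national users that their sampling error is negligible.

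- Standard error = 1/√20 = 0.22 SD.
- 95% half-width = 1.96 × 0.224 = 0.44 SD.
- Power for 0.3 SD, two-sided alpha 0.05: 0.3/0.224 = 1.34, and Φ(1.34 - 1.96) = Φ(-0.62), about 27%.

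These are best-case values, and they apply equally to the planned contrast and to the alternative.

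**The case against.** **The comparison may be meant as a benchmark.** If controls without the app behave like app users, measurement may be acting much as the app does. The plan states no interpretation rule, so this reading is open, and it would be wrong to say that the authors would call any difference reactivity. It still does not identify R: agreement also arises when A and R are both zero, and A is itself what Aim 2 explores.

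**R could be recovered by combination.** Adding the randomized Smoke Sense minus control contrast (A) to the planned one gives A + (R - A + S) = R + S. This is correct under additivity and comparable measurement of outcomes. It is algebraically the like-for-like contrast, and the plan does not state the step.

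**The alternative has its own faults.** This stands. Trial participants are recruited through Spokane colleges, trained on the app and paid up to $150, so it would be wrong to infer that the two groups differ only in study participation. National users who report in the app are already being measured, so the contrast captures only an increment. Reactivity in people without the app could differ.

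**The instruments might agree.** Controls answer Qualtrics surveys and national users report in an app tab, but survey items could be written to match. A mismatch is therefore likely but not established; what is certain is that the matched outcomes are undefined.

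**The consequence is small.** This also stands. A reader might infer that the check could lead the sponsor to the wrong control condition for the next trial. The documents do not support that: section 4.4 already commits to a future attention control, whatever the check shows.

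**Conclusion.** The concern holds, as a minor point. Taken alone, the planned contrast estimates R - A + S and cannot show whether data collection changes behavior: no difference is compatible with any R = A, and a difference is compatible with R = 0. The app-exposure mismatch follows from the text and needs no numerical assumption. The algebraic form rests on additivity and on national users receiving no trial data collection, which the documents imply without stating. The 0.3 SD values are illustrative only.

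Changing the comparator removes A and leaves R + S, with a 95% half-width of about 0.44 SD at best. The result would be descriptive and could not exclude moderate reactivity. The randomized comparisons are unaffected, because the reactivity check is separate from them. The Aim 2 and 3 tests are in any case labelled hypothesis-generating.

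**What to change.** In the section 4.4 paragraph on potential problems, make the trial's Smoke Sense arm the comparator for national users, or add it beside the control arm. Smoke Sense Plus is not suitable, since it carries content that national users are not described as receiving.

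Specify the following:

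1. **Outcomes:** the in-app weekly symptom and exposure-reduction reports, taken from the same tab in both groups.
2. **Matching:** age, asthma, area and calendar weeks. Section 4.2.a says that the app profile holds age, zip code and pre-existing conditions. Whether asthma can be picked out among those conditions should be confirmed.
3. **Interpretation:** the contrast estimates only the added effect of trial data collection among people already self-reporting in the app. It assumes additivity, still carries selection through recruitment source, app training and incentives, and is non-randomized, descriptive and imprecise. Report it with a confidence interval.

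If the control-arm comparison is kept, label it a benchmark and say that it does not isolate the data-collection effect. If matched national data cannot be obtained, state that reactivity cannot be assessed in this study.

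The comparator change costs about one sentence, and the limits a few lines more. No new data collection from participants is needed: section 4.2.a already links app data to the study ID, and the present plan already presumes access to national-user data.
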